4. ENDPOINT(S)

4.1. Primary Endpoints

- Change in global measure of cognition as measured by the Alzheimer's disease Assessment Scale-Cognitive (ADAS-Cog-13) in subjects with aMCI and mild AD between baseline and visit 7 and between baseline and visit 10.
- Change in Clinical Dementia Rating-Sum of Boxes (CDR-SOB) between screen/baseline and final assessment visit.

- Change in daily functioning as measured by the Functional Assessment Questionnaire (FAQ) in subjects with aMCI and mild AD between baseline and final assessment visit.

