12.2. Statistical Analysis of Efficacy Outcomes

Previous research has shown that the primary outcomes (ADAS-Cog 13, CDR-SOB, and FAQ) to be highly correlated. Therefore, to increase power and account for this correlation, the primary analysis will be a multivariate, linear mixed-effects regression. Specifically, the change in cognition and function measures between baseline and week 12 and between baseline and week 24 will serve as the primary outcome variables. We will include intervention arm, intervention week, intervention arm*week, age, and baseline test scores as fixed effects. The efficacy of intranasal (IN) insulin on cognition and function will be tested on the intervention arm*week interaction. Age and baseline test scores are included because of the possibility of unequal baseline values. Random intercept effects will be included to account for the nested structure of the data, multiple outcomes and observation points.

First, the assumptions of such a model will be verified. That is, the dependent variables will be tested for: (1) multivariate normality, (2) homoscedasticity, (3) equality of covariance matrices, and (4) independent observations. These outcome variables have been analyzed after log-transformation in previous studies because they have a distribution skewed to the right. We will confirm that this transformation is suitable for our study. If outcome variables are log-transformed, efficacy measures will correspond to percent change of cognitive outcomes.

To protect against type I error, efficacy of IN insulin will be considered if an overall cognitive decline is observed relative to placebo. Efficacy measures for composite cognitive and functional decline with corresponding 95% confidence intervals and p-values will be reported.

For the analysis of secondary cognition and function measures (Digit Span, Trailmaking, COWAT, Animal Naming, and WMS), secondary mood measure (GDS), and exploratory smell measure (AST) we will follow the same approach as for the primary outcomes. We have not included these tests as primary endpoints because they measure more specific effects of AD language, memory, mood, or olfaction impairment and, therefore, may be less sensitive to overall cognitive change in MCI/AD patients. Each outcome measure will be tested in its own linear mixed-effects regression model with measures from baseline to week 12 and baseline to week 24 as the outcome variables. The efficacy of IN

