insulin on each measure will be tested on the intervention arm*week interaction. Efficacy measures with corresponding 95% confidence intervals and p-values will be reported.

Exploratory measures of sleep (Sleep Questionnaire and ESS) and biomarkers (CSF Abeta, tau, and phosphotau) will follow the same approach as for the primary outcomes. Two multivariate linear mixed-effects regression models will be fit with change in either sleep or biomarker measures from baseline to visit 7 and baseline to visit 10 as the outcome variables. The efficacy of IN insulin on sleep will be tested on the intervention arm*week interaction. Efficacy measures for composite sleep decline with corresponding 95% confidence intervals and p-values will be reported.

Exploratory PET metabolism will be measured in four cortical ROIs primarily affected by AD: precuneus, posterior cingulate, and bilateral parietotemporal. A multivariate regression model will again be applied to the imaging outcome measures. Specifically, standardized change in posterior cerebral metabolism in the four ROIs from baseline to 6 months will serve as the outcomes. Intervention arm, age, and baseline test scores will be used as fixed effects. Tests of assumptions and interpretation will be similar to that described for primary outcomes. Overall cerebral metabolism and metabolism at each of the four cortical ROIs efficacy measures with corresponding 95% confidence intervals and p-values will be reported.

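### The primary efficacy test (arm*week on change scores at weeks 12 and 24) asks whether the arm difference changes after week 12, not whether glulisine works

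*Combined protocol and SAP*

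**What the plan says.** Section 12.2 (Statistical Analysis of Efficacy Outcomes) describes a multivariate linear mixed model for ADAS-Cog 13, CDR-SOB and FAQ. On the dependent variables it says that "the change in cognition and function measures between baseline and week 12 and between baseline and week 24 will serve" as the primary outcomes. The fixed effects are arm, week, arm by week, age and baseline score, with random intercepts. The test is then named: "The efficacy of intranasal (IN) insulin on cognition and function will be tested on the intervention arm*week interaction".

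Two paragraphs later there is a second criterion: "efficacy of IN insulin will be considered if an overall cognitive decline is observed relative to placebo". It comes with a promise of composite estimates, confidence intervals and p-values, but no coefficient, contrast or week.

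The interaction test is repeated for the secondary outcomes and smell ("insulin on each measure will be tested on the intervention arm*week interaction") and for sleep ("The efficacy of IN insulin on sleep will be tested on the intervention arm*week interaction"). The PET model in the same section has a single change score and uses arm without week.

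Section 4.1 defines the ADAS-Cog endpoint "in subjects with aMCI and mild AD between baseline and visit 7 and between baseline and visit 10". For CDR-SOB it is "Change in Clinical Dementia Rating-Sum of Boxes (CDR-SOB) between screen/baseline and final assessment visit", and FAQ is likewise assessed at the final assessment visit only.

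**The concern.** An arm-by-time interaction tests treatment efficacy when baseline is one of the time points in the outcome vector, because the arms are then expected to coincide at the first time point. Here baseline has been subtracted out and also used as a covariate. The only times left in the outcome are weeks 12 and 24, so the interaction compares the treatment effect at one post-treatment visit with the effect at another.

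The primary conclusion would therefore depend on when the benefit appears. Section 1.1 gives reason to think it could appear early: it cites memory effects of other intranasal insulin within 15 minutes and over 21 days. The acute glulisine pilot was largely negative, so onset is unsettled. The primary test should not depend on it.

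The two criteria in Section 12.2 can also disagree, and nothing says which one decides. That leaves the choice open after the data are seen.

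**Working it through.** **Inputs.** From Sections 12.1 and 12.4: 45 per arm, two-sided 0.05, and SD and difference of 4.6 and 3 (ADAS-Cog 13), 1.3 and 1.5 (CDR-SOB), 3.6 and 2 (FAQ). Assumed, because the documents give no value: a correlation rho between the week-12 and week-24 changes of 0.5, 0.7 or 0.9. Also assumed: the Section 12.4 SDs apply to change scores at each visit. The table prints them beside control means and does not say.

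**Step 1: reproduce the plan's power.** Two-sample t-test at one time point, noncentral t, 88 df, noncentrality d / (s·√(2/45)):
- ADAS-Cog 13: 3 / 0.970 = 3.094, power 86.426% (printed 88.426)
- CDR-SOB: 1.5 / 0.274 = 5.473, power 99.972% (printed 99.972)
- FAQ: 2 / 0.759 = 2.635, power 74.100% (printed 74.100)

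Two rows match to every digit. The ADAS-Cog row differs by exactly 2 points, perhaps a one-digit slip. The table is thus a simple two-group comparison, not the interaction.

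**Step 2: what the tested coefficient is.** Let D12 and D24 be the arm differences in change (placebo minus glulisine, so a benefit is positive on these scales). With two levels of week, coded as categories or as a number, the arm*week term is D24 − D12, up to scaling. For one outcome its per-subject SD is s·√(2(1−rho)).

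**Step 3: benefit complete by week 12 and maintained.** D24 − D12 = 0, so the rejection rate is 5% for every s, d and rho, provided the variance model is correct. A random-intercept model fitted to 400 simulated ADAS-Cog trials (D12 = D24 = 3, rho 0.5) rejected on the interaction in 3.5%, on the week-24 contrast in 89% and on the two-visit average in 96%.

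**Step 4: linear growth (D12 = D24/2).** Example, ADAS-Cog at rho 0.5: interaction SD 4.6·√1 = 4.6, noncentrality 1.5 / 0.970 = 1.547, power 33%. The averaged contrast (D12 + D24)/2 has SD s·√((1+rho)/2).

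| Power, rho 0.5 / 0.7 / 0.9 | ADAS-Cog 13 | CDR-SOB | FAQ |
|---|---|---|---|
| Interaction, maintained | 5% | 5% | 5% |
| Interaction, linear growth | 33 / 51 / 93% | 77 / 94 / 100% | 26 / 39 / 83% |
| Averaged contrast, maintained | 94 / 91 / 88% | about 100% | 85 / 81 / 76% |
| Averaged contrast, linear growth | 75 / 70 / 65% | 99.7 / 99.3 / 98.6% | 62 / 56 / 52% |
| Week-24 contrast, either pattern | 86.4% | 99.97% | 74.1% |

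**Step 5: waning benefit (full at week 12, half at week 24).** D24 − D12 = −d/2. The rejection rates equal the linear-growth row, but almost every rejection has its sign against the drug, although the drug helps at both visits.

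**Step 6: pooling the three outcomes.** The plan gives no scale for pooling, so this is illustrative: the equal-weight mean of the standardised outcomes, with correlation c between outcomes of 0.3 to 0.9 (assumed). The mean standardised effect is (3/4.6 + 1.5/1.3 + 2/3.6)/3 = (0.652 + 1.154 + 0.556)/3 = 0.787, with variance (1+2c)/3. For a maintained effect, the interaction still has 5% (4.9% to 5.2% in 20,000 simulated trials per setting), against 97% to 99.9% for the week-24 contrast. Under linear growth the interaction has 48–72%, 69–90% and 99–100% at rho 0.5, 0.7 and 0.9.

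**The case against.** The strongest reply is that the literal reading may not be what was meant. Section 12.2 says the outcomes are right-skewed and were log-transformed in earlier work, and that "If outcome variables are log-transformed, efficacy measures will correspond to percent change of cognitive outcomes". Change scores can be zero or negative and cannot be logged directly, so that sentence suits raw scores. With baseline as an outcome row, arm*week would be a valid efficacy test. The authors may also have meant week-specific arm differences built from the interaction terms. Both are possible, but the stated outcomes are changes, baseline is a stated covariate, and no week-specific contrast is named. On any of these readings the text has to be corrected.

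The second reply concerns the size, and part of it stands. Only the 5% result is free of the SD and rho assumptions. If the Section 12.4 SDs are raw-score SDs and all visits correlate at 0.9, the unadjusted week-24 change contrast has essentially 100% power for every outcome, while the linear-growth interaction has 93% for ADAS-Cog and 83% for FAQ. On the change-SD reading, the interaction at rho 0.9 equals or beats the week-24 contrast under linear growth, so it is not always the weaker test. Pooling without standardising lowers the pooled week-24 power to 91% to 98.8%. None of this alters the maintained-effect result.

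Third, the Section 4.1 timing mismatch is minor. Section 5.1, the visit schedules and the neuropsychological assessment table (Section 7.4) have CDR and FAQ collected at both Visit 7 and Visit 10, so the data exist for either contrast.

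**Conclusion.** The concern holds, and it is a must-fix because it affects the single test of the primary objective. As written, the test cannot detect a benefit that is complete by week 12 and maintained: it rejects at about 5%, where the week-24 comparison would have 74% to over 99.9% power on the plan's own inputs. That conclusion needs only the stated model and a correct variance structure. The losses under gradual onset are illustrative and depend on the assumed rho and on reading the Section 12.4 SDs as SDs of change.

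The *overall* decision rule does not rescue the plan. It names no term, and taken literally a decline relative to placebo points to harm. The same fault carries into the secondary, smell and sleep models.

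**What to change.** Keep the model and prespecify, before unblinding, one arm contrast on change from baseline as the efficacy test:
- (a) the arm difference at week 24 (arm plus arm*week at week 24), which is the comparison Section 12.4 powers; or
- (b) the arm difference averaged over weeks 12 and 24.

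Then:
- State the scale on which the three primary outcomes are pooled.
- Say that the *overall* decision rule refers to this contrast, and give the direction that counts as benefit.
- Report arm*week as supportive.
- Use the same contrast in the secondary, smell and sleep models.
- Align Section 4.1. As worded, its CDR-SOB and FAQ endpoints point to (a), while ADAS-Cog lists both visits, which is closer to (b). One pooled contrast cannot follow both.
- In Section 12.4, say whether the SDs are of change.

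If a raw-score model with baseline as a time point was intended, say so, remove the baseline covariate and name the contrast in that model.

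The cost is one decision, revised wording in Sections 4.1, 12.2 and 12.4, and the matching contrast statement in the code. No new data or participants are needed.

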12. DATA ANALYSIS AND STATISTICAL CONSIDERATIONS

12.1. Analysis Overview

Measures of central tendency and spread will be computed for the study population and by treatment group for each outcome variable. These summaries will describe patient characteristics, confirm that randomization produced a balanced design, and confirm that the planned analyses are appropriate for the distribution of the outcome variables.

Missing data are expected to be minimal. Therefore, the primary analyses will follow an intent-to-treat principal and include all randomized subjects regardless of intervention compliance and missing data. We will use linear mixed models, an analytic approach that can accommodate unbalanced data and use all available observations in the analysis by assuming data are missing at random. Sensitivity analyses will include evaluation of missing assumptions using pattern mixture models and multiple imputation and a per-protocol approach to accommodate subjects who do not adhere to the intervention protocol.

All statistical tests will be conducted in SAS Version 9.4 and will be evaluated using a two-sided 0.05 level of significance.

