12.4. Study Power

A total of n=90 subjects will be randomized to receiving either IN glulisine (n=45) or placebo (n=45) two times daily. The study is powered on the three primary outcomes, ADAS-Cog 13, CDR-SOB, and FAQ.

	Control Group Mean	Standard Deviation	Minimum Detectable Difference	Power
ADAS-Cog 13	19.2	4.6	3	88.426
CDR-SOB	7.9	1.3	1.5	99.972
FAQ	11.56	3.6	2	74.100

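### Section 12.2 does not say what the random intercepts group or what the residual covariance is, so the size of the primary arm*week test depends on the reading

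*Combined protocol and SAP*

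**What the plan says.** Section 12.2 motivates a joint model by stating "Previous research has shown that the primary outcomes (ADAS-Cog 13, CDR-SOB, and FAQ) to be highly correlated". On the responses it says "the change in cognition and function measures between baseline and week 12 and between baseline and week 24 will serve as the primary outcome variables", which makes six values per subject. On the mean model it says "We will include intervention arm, intervention week, intervention arm*week, age, and baseline test scores as fixed effects". No outcome-specific arm*week term is listed, and efficacy is judged on arm*week.

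The covariance gets one sentence: "Random intercept effects will be included to account for the nested structure of the data, multiple outcomes and observation points". Sections 12.1 and 12.2 do not name the units that receive an intercept. They also give no residual covariance, degrees-of-freedom method, robust standard error or rule for non-convergence. The assumption checks include "2) homoscedasticity, (3) equality of covariance matrices, and (4) independent observations".

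Tests "will be evaluated using a two-sided 0.05 level of significance" (section 12.1). The sleep analysis takes the same approach: "Two multivariate linear mixed-effects regression models will be fit with change in either sleep or biomarker measures".

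**The concern.** Arm*week compares the arms on the difference between the week-24 and week-12 values, so it is a within-subject contrast. An intercept that takes the same value at both weeks drops out of that difference, whether it belongs to the subject or to the subject and outcome. It can therefore tell the model nothing about whether one subject's changes in ADAS-Cog 13, CDR-SOB and FAQ move together. If the residuals are also independent, the model counts three changes per subject as three independent pieces of information.

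The joint model was chosen to handle correlation between the outcomes. On this reading it omits that correlation from the one standard error on which efficacy is decided. If the changes are positively correlated, that standard error is too small, the p-value is too small and the 95% interval is too narrow. Because the text does not fix the structure, the choice could also be made after the data are seen.

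**Working it through.** **Inputs from the documents.** 45 per arm and two-sided 0.05 (sections 12.4 and 12.1); three outcomes at two weeks (12.2); SDs 4.6, 1.3 and 3.6 (12.4).

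**Assumptions.** A common correlation r between the three week-12-to-24 changes; a single arm*week effect across outcomes; no missing data; no true effect; no covariates. For the raw scale, the SDs of the changes are taken to be in the ratio 4.6 : 1.3 : 3.6. Section 12.4 does not identify its SDs as those of changes.

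**The plan's own figures.** The plan states no size for the joint model beyond the nominal 5%. The power table reproduces as three separate two-sample t-tests with 45 per arm: CDR-SOB 99.972% and FAQ 74.100% match exactly, and ADAS-Cog 13 comes to 86.426% against the stated 88.426%. That difference does not bear on this point. The table involves no correlation between outcomes, so it gives no value of r.

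**Closed form for subject plus subject-by-outcome intercepts, independent residuals.** Let s1, s2, s3 be the SDs of the changes.
- True variance of the sum of a subject's three changes: Σs² + 2r·Σ(s_j·s_k).
- Variance the model uses: Σs².
- Equal scales: ratio = (3 + 6r)/3 = 1 + 2r.
- Raw scales: Σs² = 21.16 + 1.69 + 12.96 = 35.81, and Σ(s_j·s_k) = 5.98 + 16.56 + 4.68 = 27.22. Ratio = 1 + (2 × 27.22/35.81)r = 1 + 1.52r.
- Size = 2 × (1 − Φ(1.96/√ratio)).

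| r | Ratio, raw | Size, raw | Ratio, equal | Size, equal |
|---|---|---|---|---|
| 0 | 1.00 | 5.0% | 1.00 | 5.0% |
| 0.1 | 1.15 | 6.8% | 1.20 | 7.4% |
| 0.2 | 1.30 | 8.6% | 1.40 | 9.8% |
| 0.3 | 1.46 | 10.4% | 1.60 | 12.1% |
| 0.5 | 1.76 | 14.0% | 2.00 | 16.6% |

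Example at r = 0.5 on equal scales: √2 = 1.414, 1.96/1.414 = 1.386, two-sided tail 16.6%.

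**Simulation of the readings** (45 per arm, 10,000 trials per setting, r from 0 to 0.5, varying the stable outcome-specific variance):
- Subject plus subject-by-outcome: 16.3% to 16.6% (equal scales) and 13.5% to 14.2% (raw) at r = 0.5, agreeing with the formula.
- Subject only: 0.7% to 5.2% at r = 0 and 8.0% to 21.6% at r = 0.5 (equal scales); 0.7% to 3.3% and 4.6% to 13.1% (raw).
- Subject, subject-by-outcome and subject-by-visit: 4.6% to 5.5% throughout. This is the t-test on the subject's mean change.

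A separate simulation of subject plus subject-by-visit, without subject-by-outcome, gave 0.1% to 5.3%. When stable outcome-specific variance is large, the visit component is estimated at zero and the test becomes very conservative.

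**Fitted mixed models.** 213 REML fits at r = 0.5 on equal scales rejected in 18.8% with subject plus subject-by-outcome intercepts and in 7.0% once subject-by-visit was added. The Monte Carlo standard errors are about √(0.166 × 0.834/213) = 2.5 points and √(0.05 × 0.95/213) = 1.5 points, so both agree with the larger simulation.

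**The case against.** The strongest reply is that the plan never states the structure that does the damage. The sentence speaks of intercept effects in the plural and mentions observation points, so a subject-by-visit intercept is a fair reading. Together with subject-by-outcome intercepts it holds the size near 5%. The residual covariance is unstated, not stated to be independent, and a model called multivariate may be meant to carry a multivariate residual. All of this stands: the defect is conditional on the reading.

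The second reply is that r is unknown. The plan calls the outcomes highly correlated, but the test depends on the correlation of their changes between weeks 12 and 24. If the outcomes correlate only through a stable subject component, differencing removes it, r is 0 and the test is exact. This also stands, and is why the table starts at r = 0.

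Third, a joint test of outcome-specific arm*week terms would inflate less: 4.8% to 7.0% on equal scales and 6.8% to 8.4% on raw scales. But the listed fixed effects contain no such terms, and section 12.2 reports a composite effect. Log-transformation, which the plan allows, would change the SD ratio. For a common r, equal scales give the largest ratio, so the equal-scale column is an upper bound for this reading.

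A reader might also infer that the homoscedasticity and independence checks must fail because the three scales have different SDs and each subject gives six values. The text does not support that. The checks can equally mean equal variance across arms within an outcome, and independence between subjects.

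**Conclusion.** The concern holds in conditional form. Section 12.2 leaves the covariance of the primary model open, and the size of its efficacy test depends on how the gap is filled. With subject and subject-by-outcome intercepts and independent residuals, a literal reading of the text, the size is 5% at r = 0, about 9% to 10% at r = 0.2 and about 14% to 17% at r = 0.5. The matching coverage of the 95% interval is 100% minus these figures. With a subject-only intercept the error can go either way. Of the readings simulated, only subject-by-outcome plus subject-by-visit intercepts kept the size near 5% at every setting.

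A reader might infer that the planned test simply runs at an inflated level, or that false claims of efficacy will be two to three times as frequent as intended. The documents support neither. They do not fix the intercept levels, the residual structure or r, and one permitted reading is sound. The figures rest on the assumptions listed above; baseline adjustment and dropout were not modelled.

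This is still more than missing detail. Literal readings of the stated method give a wrong standard error for the trial's primary test. The sleep model inherits the problem, but it is exploratory. The secondary outcomes are fitted one at a time, so they have no cross-outcome correlation to omit.

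**What to change.** Replace the random-intercept sentence in section 12.2 with wording such as: *The three outcomes are put on a common scale before modelling. The six outcome-by-week values of a subject have an unstructured covariance matrix, or an outcome-by-week Kronecker structure (UN@UN). Degrees of freedom are Kenward-Roger. If the model does not converge, subject-clustered sandwich standard errors are used.*

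Choose one of the two structures in advance and name the common scale. The unstructured form has 6 × 7/2 = 21 covariance parameters for 90 subjects; the Kronecker form has 6 + 3 − 1 = 8. Apply the same rule to the exploratory sleep model. The assumption checks may stay.

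The cost is SAP wording and a REPEATED statement in the SAS program already planned. No patients or data are added. The confidence interval may be wider than under a random-intercept model that leaves the correlation out.

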	References	32

DEFINITIONS

Adverse event (AE) – any undesirable patient experience that may include but is not limited to an abnormal sign, symptom, illness, abnormal laboratory value, or other medical event.

ADAS-Cog 13 - an outcome measure for global cognition in clinical trials for Alzheimer's Disease.

Amnesic Mild Cognitive Impairment (aMCI) - A condition characterized by subject memory complaints and objective neuropsychological testing demonstrating abnormalities >1.0 SD affecting memory. There is preservation of instrumental activities of daily living without functional limitations. This population has a 40% chance of developing Alzheimer's Disease over a 2 year period.

Alberta Smell Test (AST) - A test to identify the olfactory abilities of an individual.

Alzheimer's disease (AD) – A chronic progressive neurodegenerative condition resulting in memory impairment, loss of function, and progressive deterioration in other cognitive domains including language, perceptual skills, attention, construction, orientation, and problem solving.

Animal Naming - a word fluency test measuring executive functioning and language ability.

Mild Alzheimer's disease - Patients meeting NINCDS-ADRDA criteria for probable AD with a CDR=1

Columbia-Suicide Severity Rating Scale (C-SSRS) - A scale designed to quantify the severity of suicidal ideation and behavior.

Controlled Oral Word Association Test (COWAT) - a short, paper/pencil measure of phonemic fluency and executive functioning from the Multilingual Aphasia Examination.

Clinical Dementia Rating (CDR) - a numeric scale used to quantify the severity of symptoms of dementia (i.e. stage).

Data Safety Monitoring Board (DSMB) - an independent group assigned to review safety data to monitor for incidence of trends that would warrant termination of the trial.

Diagnostics and Statistical Manual-IV(DSM-IV TR) – a diagnostic manual published by the American Psychiatric Association that provides a common language and standard criteria for the classification of mental disorders including Alzheimer's Disease.

Digit Span subtest from the Wechsler Adult Intelligence Scale -4th Edition (WAIS-IV) - is a brief measure of auditory attention, concentration, and working memory.

Epworth Sleepiness Scale (ESS) – A measure to identify excessive daytime sleepiness.

Geriatric Depression Scale (GDS) - a screening test for depression in older adults.

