Clinical trials of intranasal insulin in AD have demonstrated therapeutic effects involving memory, attention and cognition without significantly altering serum insulin or glucose levels. A clinical trial consisting of 26 memory impaired subjects (13 with AD and 13 with mild cognitive impairment) and 35 normal controls showed that IN insulin 20 IU or 40 IU resulted in improvements on two declarative memory tasks compared to placebo within 15 minutes of drug administration (29). IN insulin administered at 20 IU resulted in greater story recall whereas doses at 40 IU more favorably improved word list recall. There was no impact on IN insulin on serum glucose or insulin levels. Another study of 24 early AD/mild cognitive impairment subjects showed that 20 IU BID of intranasal insulin resulted in sustained benefit in over a 21 day period (30). Furthermore, IN insulin induced favorable changes in the serum amyloid-beta 40/42 ratio while having no impact on systemic glucose or insulin levels. Most recently, Craft and colleagues have shown improved memory and function as represented by the ADAS-Cog and ADCS-ADL, respectively in AD patients treated during a four month clinical trial (31). These changes in memory and function were associated with favorable changes in CSF tau and tau-Ab42 ratio. Additionally, IN insulin minimized progression in loss of cerebral hypometabolism as measured by FDG-PET.

Therapeutic response to IN insulin may be modified by both insulin type as well as ApoE4 carrier status. A study of 38 normal subjects showed that rapid-acting insulin aspart (Insulin NovoLog HM, Novo Nordisk) resulted in greater declarative memory improvements compared to regular insulin over 8 an week period (32). Additional clinical trials have suggested memory benefits associated with IN insulin are diminished among ApoE4 carriers diagnosed with AD (29).

Glulisine is a rapidly absorbed insulin analogue lacking the zinc ingredient commonly found in insulin formulations. This analogue differs from human insulin in that the amino acid asparagine at position B3 is replaced by lysine and the lysine in position B29 is replaced by glutamic acid. For this study, we have chosen glulisine due to prior speculation that zinc-containing compounds may be toxic to olfactory neurons (33, 34) as well as prior studies demonstrating improvements in declarative memory with RA compared to regular insulin.

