7.4.1. ADAS-Cog 13 Summary

The ADAS-Cog was developed as an outcome measure for global cognition in clinical trials for Alzheimer’s disease. The ADAS-Cog assesses multiple cognitive domains including memory, language, praxis, and orientation (47). Overall, the ADAS-Cog has proven successful for its intended purpose with higher scores indicating greater cognitive impairment. The modified ADAS-Cog 13-item scale (48) includes all original ADAS-Cog items with the addition of a number cancellation task and a delayed free recall task, for a total of 85 points. The purpose of these additional items increases the number of cognitive domains and range of symptom severity to best assess subjects affected by the earlier stages of Alzheimer’s disease (e.g. amnesic MCI and mild AD).

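### Section 12.2 words the efficacy criterion in the wrong direction, and no other section says which sign of the treatment effect counts as success

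*Combined protocol and SAP*

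**What the plan says.** Section 12.2 fits one multivariate linear mixed model to ADAS-Cog 13, CDR-SOB and FAQ and names the term to be tested: "The efficacy of intranasal (IN) insulin on cognition and function will be tested on the intervention arm*week interaction". It then gives the condition under which efficacy is to be concluded, introduced as a safeguard on type I error: "efficacy of IN insulin will be considered if an overall cognitive decline is observed relative to placebo". The next sentence sets out the reporting: "Efficacy measures for composite cognitive and functional decline with corresponding 95% confidence intervals and p-values will be reported".

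Section 12.1 fixes the level for all tests, which "will be evaluated using a two-sided 0.05 level of significance". On scoring, Section 7.4.1 describes the ADAS-Cog "with higher scores indicating greater cognitive impairment". Section 7.4.6 orders the global CDR from very mild to severe as the number rises, and forms the sum of boxes by adding the six domain ratings. Section 7.4.9 describes what the FAQ measures but not which way it is scored.

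**The concern.** The subject of the sentence is intranasal insulin and the comparator is placebo. The plain meaning is therefore that efficacy is concluded when cognition declines on insulin relative to placebo, which is harm. A trial in which glulisine slowed decline would not meet the condition as written.

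This is not a loose remark in the background. It is the plan's decision rule for the primary analysis, and it is offered as the protection against a false positive claim. A pre-specified rule should be applicable as it stands. This one works only if the reader assumes that it means the opposite of what it says.

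**Working it through.** **1. What the word decline means here.** The inversion would disappear if decline meant a fall in score, because a lower ADAS-Cog score is better. The text does not support that. The sentence speaks of cognitive decline, not of a score. The following sentence uses the same word for cognitive and functional worsening, and Section 12.2 later uses it in the same way for sleep. On the ADAS-Cog (Section 7.4.1), cognitive decline is a rise in score.

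**2. Whether another section supplies the sign.**
- Section 3.1 sets the primary objective as measuring effects, with no direction.
- Section 4.1 defines the primary endpoints as change, with no favourable direction.
- Section 12.2 tests the arm-by-week interaction without a sign.
- Section 12.1 makes the test two-sided, so the p-value carries no direction.
- Section 12.4 lists unsigned detectable differences. Power is the same for benefit and for harm of equal size, so the table does not show which was meant.

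**3. What the trial expects.** Section 1.1 reports: "Clinical trials of intranasal insulin in AD have demonstrated therapeutic effects involving memory, attention and cognition". The expected direction is improvement. This shows that the sentence contradicts the trial's purpose, but it does not state a rule.

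**4. Which tail the sentence names.** The inputs are from Section 12.4: 45 per arm, with the difference d and standard deviation SD for each outcome. The level is two-sided 0.05, from Section 12.1. The sentence names no significance threshold, so I assume it is applied together with that level.

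The noncentrality is d / (SD × √(2/45)), with √(2/45) = 0.2108. The test is a two-sample t-test on 88 degrees of freedom. The last two columns assume a true benefit of the table's size.

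| Outcome | d | SD | Noncentrality | Plan's power | Significant, benefit tail | Significant, decline tail |
|---|---|---|---|---|---|---|
| ADAS-Cog 13 | 3 | 4.6 | 3.094 | 88.426% | 86.425% | 2.6 × 10⁻⁷ |
| CDR-SOB | 1.5 | 1.3 | 5.473 | 99.972% | 99.972% | 8.2 × 10⁻¹⁴ |
| FAQ | 2 | 3.6 | 2.635 | 74.100% | 74.099% | 2.5 × 10⁻⁶ |

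The plan's CDR-SOB and FAQ figures reproduce. Its ADAS-Cog 13 figure is 2.00 points above the t-test value and 1.28 points above the normal approximation (87.15%); nothing here depends on that gap.

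If the true effect were harm of the same size, the last two columns would swap. With no effect, each tail holds 2.5%, as in any two-sided 0.05 test. Correcting the direction changes none of these probabilities. It changes only which column is called success.

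**The case against.** The strongest reply is that the sentence affects only a label. The model, the tested term, the two-sided level and the reported estimates, intervals and p-values are all specified separately, and none changes with the faulty wording. The sentence's job is multiplicity: efficacy is to be judged on the joint effect rather than outcome by outcome. A loose reading, an effect *on* cognitive decline compared with placebo, fits that job and is probably what was meant.

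Much of this stands, and it rules out several stronger readings that a reader might infer.

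- *That the trial would in practice declare harm a success.* This assumes that someone applies an evidently inverted sentence literally. The rationale makes that unlikely.
- *That the intended sign cannot be recovered.* Sections 1.1, 7.4.1 and 7.4.6 together allow it to be inferred for ADAS-Cog 13 and CDR-SOB. Only the FAQ has no stated scoring direction.
- *That mixed scoring across the secondary measures makes a common rule unusable.* Section 12.2 fits each secondary measure in its own model, so those measures need no common sign.
- *That the power of about 86% on ADAS-Cog 13 is the chance that a real benefit would fail the rule.* That figure belongs to a single-outcome t-test. The rule concerns an overall effect from a multivariate model, for which the documents give no power.

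The reply does not rescue the sentence itself. That most readers would guess the intent is no substitute for a correct pre-specified criterion, and no other section states one.

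**Conclusion.** The criterion is wrong as written and should be corrected. The error is one of direction in the rule for concluding efficacy, most likely a drafting slip. Its effect on the stated verdict is complete, because benefit and harm change places. Its effect on estimates, intervals, p-values, sample size and alpha is nil.

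The conclusion rests on the plain meaning of the sentence, on the use of decline for worsening in the sentence that follows, and on the absence of a favourable sign anywhere else. It does not rest on the tail probabilities in the table, which are single-outcome illustrations.

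Reversing the direction does not by itself complete the rule. The sentence gives no significance threshold, and the plan does not define the overall effect. The three outcomes have standard deviations of 4.6, 1.3 and 3.6, and Section 12.2 does not say how they are put on a common scale or combined. A direction for the combined effect also needs the FAQ's direction to be known.

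**What to change.** Replace the sentence in Section 12.2 with:

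> Efficacy of IN insulin will be concluded only if the overall treatment effect from the primary multivariate model is significant at two-sided 0.05 and its direction shows less cognitive and functional worsening on glulisine than on placebo.

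Then add:

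- how ADAS-Cog 13, CDR-SOB and FAQ are put on a common scale and combined into that overall effect, naming the model term or contrast, since the section currently assigns the efficacy test to the arm-by-week interaction;
- the scoring direction of each primary outcome: higher is worse for ADAS-Cog 13 and CDR-SOB, and the FAQ direction to be stated by the sponsor.

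A line giving the favourable direction of each secondary and exploratory score would help reporting but is not needed to repair the rule.

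The cost is a few sentences, best settled before unblinding. Sample size, alpha, visits and data collection do not change.
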